Study 3: Effects of Strengthening and Stretching Exercise Programs on Pain and Gait in Patients with Plantar Fasciitis: A Randomized Controlled Trial

Study Protocol

This study was a double-blind randomized controlled trial conducted at Physical Therapy Center, Mahidol University. It aimed to compare the effects of strengthening versus stretching exercises on individuals with PF.

Participants were diagnosed with PF based on clinical symptoms and ultrasound measurement, and then were randomly allocated into two groups: strengthening and stretching. Both groups initially received standardized conservative physical therapy (therapeutic ultrasound and manual therapy) twice a week for 4 weeks. Subsequently, they followed their assigned home-based exercise program three days a week for 4 weeks, continuing independently for 2 months after supervised intervention ended. Participants and the physical therapist who provided a conservative PT intervention were blinded to group allocation.

Outcome assessments, including pain intensity via visual analog scale (VAS) and gait parameters measured on a force distribution platform, were performed at five time points: Baseline, 2 weeks after the intervention, 4 weeks after the intervention, 1-month follow-up, 2-month follow-up

Statistical Analysis Plan

Data distribution was tested for normality using the Kolmogorov-Smirnov test. Outcome measures were analyzed using two-way repeated measures ANOVA to examine:

- Main effects of time (changes across assessment points),
- Main effects of group (differences between strengthening and stretching groups),
- Interaction effects (whether changes over time differed by group).

Post-hoc Bonferroni tests identified specific time points with significant differences. Independent sample t-tests compared groups at individual assessment times. Statistical significance was set at $p < 0.05$. SPSS software was used for all analyses.

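### Study 3's post-hoc Bonferroni tests are valid, but the Holm step-down procedure would keep every rejection, hold the same familywise error and sometimes find more: an optional, cheap gain

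*Combined protocol and SAP*

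**What the plan says.** The Study 3 protocol text says that outcome assessments (pain VAS and gait parameters) "were performed at five time points", baseline included. The Study 3 Statistical Analysis Plan then gives three layers of testing:

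- Omnibus: "Outcome measures were analyzed using two-way repeated measures ANOVA to examine" the effects of time, group and their interaction.
- Post hoc: "Post-hoc Bonferroni tests identified specific time points with significant differences".
- Between groups: "Independent sample t-tests compared groups at individual assessment times".

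The significance level is 0.05. The plan names no step-down version of Bonferroni. It does not give the number of comparisons in the family or say whether the post-hoc contrasts are pooled over arms, within arm or between arms. It does not call 0.05 a familywise level; that is inferred from the choice of Bonferroni. Study 3 states no sample size, SD, effect size or power.

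**The concern.** Single-step Bonferroni holds every test in the family to the same strict threshold, even after most of the other hypotheses have been rejected. Holm relaxes the threshold as rejections accumulate and keeps the same error bound.

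The ANOVA time effect already addresses whether anything changes. The post-hoc tests are there to say which time points differ, so rejections beyond the first are what they are for. At stake is how complete that description is, for example whether an early drop in pain or a late further gain is declared as well as the large overall change from baseline.

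**Working it through.** **Inputs from the documents.** Five visits, Bonferroni post hoc, level 0.05. The plan gives no adjusted threshold or power figure to reproduce.

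**Thresholds.** Bonferroni uses α/m for every test. Holm compares the i-th smallest p-value with α/(m − i + 1) and stops at the first failure.

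- Pairwise visit contrasts: m = 5 × 4 / 2 = 10. Bonferroni uses 0.005 throughout. Holm uses 0.005, 0.0056, 0.0063, 0.0071, 0.0083, 0.01, 0.0125, 0.0167, 0.025, 0.05.
- One comparison per visit: m = 5. Bonferroni uses 0.01 throughout. Holm uses 0.01, 0.0125, 0.0167, 0.025, 0.05.

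**What holds whatever the data.**

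1. Every Holm threshold is at least α/m, so each p-value that passes Bonferroni also passes Holm.
2. Both methods need the smallest p-value to be at most α/m before anything is rejected, so the chance of at least one rejection is identical.
3. Suppose m0 hypotheses are true nulls. The first of them to be rejected comes no later than step m − m0 + 1, so its p-value is at most α/m0. The chance that any of m0 null p-values is that small is at most m0 × α/m0 = α, under any dependence. Holm therefore has the same 5% bound.

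**Size of the gain, m = 10 (all inputs assumed).** Paired t-tests between visits pooled over arms, multivariate normal VAS with SD 2, N = 30, 40 or 60, within-person correlation 0.5 or 0.7, 4,000 simulated trials per scenario. Power is averaged over the contrasts that truly differ. Columns 2 to 4 are for N = 40 and correlation 0.5; the last column covers all N and correlations.

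| Visit means | Bonferroni | Holm | Trials with an extra true difference | Gain, points |
|---|---|---|---|---|
| 6, 5, 4.3, 3.8, 3.4 (all 10 non-null) | 62% | 68% | 48% | 6 to 8 |
| 6, 5, 4, 4, 4 (7 non-null) | 76.3% | 81.8% | 32% | 1 to 6 |
| 6, 5.5, 5, 5, 5 (7 non-null, smaller effects) | 30.0% | 32.0% | 13% | 2 to 5 |
| 6, 4, 4, 4, 4 (early response, then plateau) | 99.9% | 100% | 0.1% | near 0 |

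Hand check of one contrast in the first row, baseline against the second visit. The SD of the difference is 2 × √(2 × (1 − 0.5)) = 2 and the standard error is 2/√40 = 0.316, so the expected t is 1.0/0.316 = 3.16. The two-sided 0.005 critical value on 39 degrees of freedom is about 2.98. Power is roughly Φ(3.16 − 2.98) = Φ(0.18) = 57%, which matches the simulated 57% for Bonferroni. Holm gives 70% for the same contrast.

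For the patterns with three equal visit means, simulated familywise error was at most 1.7% with Bonferroni and 4.3% with Holm, both below 5%.

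**Size of the gain, m = 5 (assumed).** Give each true effect 80% power at an unadjusted two-sided 0.05 (noncentrality 2.8), with correlation between tests of 0, 0.5 or 0.8. Bonferroni power per true effect is Φ(2.8 − 2.576) = Φ(0.224) = 59%. Holm gives 59% with one true effect, 62 to 63% with three and 67 to 70% with five. If the five tests are between-group comparisons, baseline is one of them, and randomisation leaves no true difference there. At most four can then be non-null, so the five-effect figure is a ceiling that is not reached.

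**The case against.** The strongest reply is that nothing here is wrong. Bonferroni controls familywise error, the plan contradicts no target of its own, and the same remark could be made of any plan that uses Bonferroni. That stands. A reader might infer that the trial will miss real changes. The documents do not support this: they give no N, SD, correlation or expected profile, so a missed difference is only a probability under assumed inputs. The larger single-contrast gains, such as 57% to 70%, come from the pattern most favourable to Holm.

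A reader might also infer that the comparison of strengthening with stretching is underpowered because of this choice. If the sentence means contrasts between visits, as its wording suggests, that comparison rests on the group and interaction terms and the visit-wise t-tests, and Holm leaves all of these untouched. Only if the Bonferroni family is the set of between-group tests would the gain bear on it.

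Nor does Holm cure the separate matter of the visit-wise t-tests, for which no adjustment is stated. If each of the five is run at 0.05, their familywise error is up to 5 × 0.05 = 25%, or 1 − 0.95^5 = 22.6% if independent, whichever post-hoc method is used between visits.

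Bonferroni also gives simple simultaneous confidence intervals, which Holm does not. The plan mentions only p-values, but silence in a short summary does not show that intervals were not intended. Finally, the plan is written in the past tense. If results have been seen, moving to a procedure that can only reject more is a post-hoc choice. The documents do not settle this.

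What remains is that, for declaring which time points differ, Holm is never worse under either reading of the family.

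**Conclusion.** The point holds as an optional efficiency improvement, not as an error. That Holm keeps every Bonferroni rejection at the same familywise bound needs no assumptions and is true for m = 10 and m = 5. The size does rest on assumptions. For 10 contrasts under the inputs above, the average gain is about 0 to 8 points and depends mainly on how many contrasts are truly non-null and how close their power already is to 0 or 100%. Both arms receive active treatment, so change across several visits is plausible, but the documents give no expected profile and that is a judgement. Under the time-contrast reading, the benefit is a fuller account of when pain and gait change, with no effect on the randomised comparison.

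**What to change.** Replace the post-hoc sentence with:

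> Post-hoc comparisons between time points use the Holm step-down procedure on the unadjusted pairwise p-values, with familywise error 5% for each outcome.

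This also states the family, which the plan leaves open, so the sponsor should first confirm that contrasts between visits are what is meant. If the family is instead the five visit-wise comparisons, the same procedure applies with m = 5 and the sentence should say so.

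The cost is one sentence and a few lines of calculation on p-values from the same comparisons, with no new data. The downside is the lack of simple matching simultaneous intervals; if intervals are reported, show Bonferroni intervals alongside the Holm decisions. If the data have already been analysed, keep the Bonferroni result as planned and label the Holm result as post hoc.

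### Study 3 names no decisive between-group contrast and does not say whether its visit-wise group t-tests are adjusted or gated, so its false-positive risk is uncontrolled and cannot be stated

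*Combined protocol and SAP*

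**What the plan says.** Under Study 3, Study Protocol, the outcomes include "pain intensity via visual analog scale (VAS) and gait parameters measured on a force distribution platform". The number of gait parameters is not given, and no outcome is called primary. The assessments are "Baseline, 2 weeks after the intervention, 4 weeks after the intervention, 1-month follow-up, 2-month follow-up".

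The same section says that both arms first receive the same conservative therapy for 4 weeks. The arms separate only after that: "Subsequently, they followed their assigned home-based exercise program three days a week for 4 weeks".

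Under Study 3, Statistical Analysis Plan, each outcome goes into a two-way repeated measures ANOVA with time, group and interaction effects. Two sentences on follow-up tests come next: "Post-hoc Bonferroni tests identified specific time points with significant differences", then "Independent sample t-tests compared groups at individual assessment times". The significance level is 0.05 throughout. No sample size, error budget or order of testing is given for Study 3. Study 1, in the same document, does identify a main analysis.

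**The concern.** Three kinds of result could each be reported as a difference between the programmes: the ANOVA group effect, the interaction, and a t-test at any visit. Each recurs for every outcome, and nothing says which one answers the randomised question. If the programmes do not differ, the chance of at least one nominally significant group result depends on rules that the text leaves open.

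The visit labels add to this. The text does not say which intervention the 2- and 4-week visits follow. On one reading they fall within the shared therapy, before the arms have been treated differently. A group difference there could not be an effect of the assigned exercise. This also changes how many tests bear on the treatment question.

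**Working it through.** The plan states no overall error rate or power for Study 3, so there is no figure to reproduce. The calculation below is illustrative.

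**Inputs from the document.** Level 0.05 per test (two-sided assumed); two arms; five assessments, of which four are post-baseline; VAS plus gait parameters in the plural, hence at least three outcomes on a plain reading.

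**Inputs assumed.** No true difference on any outcome; 20 or 40 per arm; compound symmetry; correlation between visits 0.3-0.9; correlation between outcomes 0.3-0.7.

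**Step 1, independent tests as a rough guide.** The chance of at least one false positive in k tests is 1 - 0.95^k:
- k = 4 (one outcome, four visits): 18.5%
- k = 6 (three outcomes, two visits; or three outcomes, two ANOVA effects): 26.5%
- k = 12 (three outcomes, four visits): 46.0%

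**Step 2, allowing for correlation.** Visits and outcomes are correlated, which lowers these figures. Null trials were simulated, 20,000 per setting. The ANOVA effects were computed over all five visits and the t-tests at the post-baseline visits. Ranges run over the assumed settings.

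| Rule for the group t-tests | VAS alone | Three outcomes |
|---|---|---|
| Ungated, unadjusted, four visits | 9-17% | 20-42% |
| Ungated, unadjusted, last two visits only | not computed | 15-25% |
| Bonferroni over four visits within each outcome | 3-5% | 6-14% |
| Only after that outcome's significant interaction | 1-3% | 2-9% |
| Gate and Bonferroni together | not computed | 1-4% |

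With five outcomes the ungated, unadjusted figure is 26-59%.

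**Step 3, adding the ANOVA effects.** Three outcomes give 3 x 2 = 6 group and interaction tests. If each counts as a claim at 0.05, these alone give 21-26%. Gating the t-tests on the interaction leaves this unchanged, because a gated t-test can be significant only when a claim already exists. With ungated, unadjusted t-tests the total is 28-48%.

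**Step 4, size of the family.** The number of between-group tests is outcomes x (eligible post-baseline visits + 2 ANOVA effects). Four eligible visits give 3 x (4 + 2) = 18, or 17 after removing a primary. Two eligible visits give 3 x (2 + 2) = 12, or 11.

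**Step 5, power under Bonferroni.** For a comparison with 80% power at 0.05, power at 0.05/m is Φ(1.960 + 0.842 - z), where z is the two-sided critical value at 0.05/m:
- m = 11: 48.6%
- m = 12: 47.5%
- m = 17: 43.2%
- m = 18: 42.5%

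**The case against.** The strongest reply is that the plan has a natural reading under which the t-tests are controlled. The interaction is described as the test of whether change differs by group, which is the obvious treatment question. The t-test sentence comes straight after the Bonferroni sentence, so it may describe follow-up within the same procedure. With both an interaction gate and Bonferroni, t-test error stays at 1-4% even with three outcomes. The document is also a summary, and a fuller protocol may settle the matter.

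Much of this stands. A reader might infer that the t-tests are certainly unadjusted, or that the trial carries a false-positive risk of 20-42%. The documents support neither. The text is silent on gate and adjustment; it does not exclude them. The 20-42% range needs exactly three outcomes, four counted visits and the assumed correlations. It is not a bound in either direction.

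A reader might also infer that the 2- and 4-week visits precede any difference between the arms. The wording allows that reading but does not establish it.

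What the reply does not answer is the missing primary contrast. The interaction is listed beside the group effect with no priority. No reading of the t-test sentence controls the ANOVA effects across outcomes.

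**Conclusion.** The concern holds as a gap in specification that affects error control; it is not a demonstrated wrong test. What is certain from the text is that no primary outcome, visit or effect is named, that there are several between-group routes at 0.05, and that no gate or adjustment is stated for the group t-tests. The size is conditional on the assumptions above and on how many outcomes and visits count. The firmest part is that the strictest reading of the t-tests still leaves about 21-26% if each ANOVA group and interaction effect over three outcomes counts as a claim. The point should be corrected. Confidence is medium, because the outcome count, correlations, sample size and any fuller protocol are not available.

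**What to change.** 1. Reconcile which intervention the 2- and 4-week visits follow, and state which visits come after the arms differ. Do not count a baseline comparison as a treatment test. If the ANOVA group effect is kept as a claim, note that it averages over baseline when baseline is one of the levels.

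2. If outcome data have not been analysed by group, name one decisive between-group contrast at 0.05. Examples are the VAS group-by-time interaction, or VAS at one visit after the arms differ. Base the conclusion on it and treat everything else as supportive. If further claims are wanted, test the rest only if the primary is significant, with Holm across all remaining between-group tests, ANOVA effects included. With no true differences, a false claim then requires a false-positive primary, so the overall error is 5%. An ungated primary at 0.05 beside separately adjusted secondary t-tests does not achieve this: with three outcomes and four visits it leaves 6-9%, or 22-29% if unadjusted ANOVA effects also count.

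3. The text is in the past tense, so the analysis may already be done. A primary named after the data are seen cannot guarantee 5%. In that case report the number of between-group tests, apply Holm across all of them, and label any hierarchy post hoc. Bonferroni over 18 tests gave 2-4% in the simulation. Holm gives the same figure when nothing truly differs, since its first step is the Bonferroni threshold.

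The cost is wording or recalculated p-values, with no new data. Secondary comparisons lose power: one with 80% at 0.05 falls under Bonferroni to about 42-43% with 17-18 tests, or 47-49% with 11-12. Holm is at least as powerful. A primary named in advance keeps the full 0.05.
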